4.1. Inclusion Criteria

- 1. Males, 18 years or older
- 2. Signed and dated written informed consent by the patient prior to any study-specific procedures.
- 3. Histologically confirmed adenocarcinoma of the prostate.
 - a. biochemical recurrence: defined as PSA is ≥ 0.2 ng/mL after radical prostatectomy or PSA nadir plus 2 ng/mL after radiation therapy with corresponding CT/MRI or bone scan revealing absence of local recurrence or metastatic lesions.

OR

- b. metastatic disease: defined as both, castration-sensitive or castration-resistant mPCa (presence of at least one metastatic lymph-node, visceral metastasis and/or bone metastasis).
- c. At least 2 weeks must have elapsed between last anti-cancer treatment administration and the administration of the imaging product, ⁶⁸Ga-PSMA-R2.
- 4. Prior major surgery must be at least 12 weeks prior to study entry.
- 5. Eastern Cooperative Oncology Group (ECOG) performance status 0-2, with a life expectancy ≥ 6 months.
- 6. Adequate bone marrow reserve and organ function as demonstrated by complete blood count, and biochemistry in blood and urine at Screening:
 - Hemoglobin (Hb): >8.0g/dL

- Platelet count of $> 50.000/\text{mm}^3$
- Serum creatinine < 1.5 ´ upper limit normal (ULN) or estimated glomerular filtration rate (eGFR) > 50 mL/min based upon The Chronic Kidney Disease Epidemiology Collaboration (CKD-EPI) equation.
- 8. For male patients with partners of childbearing potential, agreement to use barrier contraceptive method (condom) and to continue its use for 28 days after IP administration.

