15.2.2. LESIONS DETECTED BY PET SCAN AND/OR CONVENTIONAL SCAN, BY TBR

The number of positive lesions detected by PET scan, correlated or not with conventional scan, will be presented by TBR category.

15.2.3. BURDEN AND LOCATION OF TUMOR LESIONS DETECTED BY ⁶⁸Ga-PSMA-R2 IN COMPARISON WITH CONVENTIONAL IMAGING MODALITIES SUCH AS CT/MRI AND/OR BONE SCAN.

- The difference of number of lesions detected by ⁶⁸Ga-PSMA-R2 PET scan and by conventional scan modalities such as CT/MRI and/or bone scan, will be displayed by location. The number of lesions detected on the PET scan, correlated and not correlated with conventional scan lesions, will be presented. The number of lesions detected on the conventional scan, not correlated with lesions detected on the PET scan, will be presented.
- The difference in the number of positive patients detected by ⁶⁸Ga-PSMA-R2 PET and by conventional scan modalities such as CT/MRI and/or bone scan, will be displayed by location. The number of positive patients detected on the PET scan, with at least 1 lesion correlated, and at least 1 lesion not correlated with a lesion detected on the conventional scan, will be presented. The number of positive patients detected on the conventional scan, with no lesions correlated with any lesion detected on the PET scan, will be presented. Note: A positive patient has at least 1 lesion detected.

15.2.4. CALCULATION OF PATIENT LEVEL AGREEMENT OF ⁶⁸Ga-PSMA-R2 PET IMAGING WITH CONVENTIONAL IMAGING IN PROSTATE CANCER PATIENTS

The patient level agreement is commonly used to characterize the agreement of a new test with the non-reference standard. Here ⁶⁸Ga-PSMA-R2 PET scan is the new test and conventional scan is the non-reference Standard.

		Conventional Scan	
		+	-
⁶⁸ Ga-PSMA-R2 PET Scan	+	a	b
	-	c	d
Total		a+c	b+d

The patient-level positive percent agreement, negative percent agreement and overall percent agreement will be calculated based on the number of patients with at least one positive lesion detected by conventional scan and/or at least one positive lesion detected by PET scan.

Document: K:\AAA\Ga-PSMA-R2\VYA27826\ Biostatistics\Documentation\SAP\v2.0\Ga-PSMA-R2-SAP_v2.0
 Author:  Version Number: 2.0

Version Date: 29JUN2020

Template No.: CS_TP_BS016 Revision 5
 Effective Date: 01Apr2018

Reference: CS_WI_BS005

These percent agreements will be calculated as follows with their two-sided 95% score confidence intervals:

- Positive percent agreement: $a/(a+c) * 100$

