- Negative percent agreement: $d/(b+d) * 100$
- Overall percent agreement: $(a+d)/(a+b+c+d) * 100$

Where

- a is the number of patients with at least one positive lesion detected by conventional scan and at least one positive lesion detected by PET scan
- b is the number of patients with at least one positive lesion detected by PET scan that is not correlated with conventional scan
- c is the number of patients with at least one positive lesion detected by conventional scan that is not correlated with PET scan
- d is the number of patients with no lesions detected by conventional scan or PET scan

These 3 coefficients and their 95% Clopper Pearson Exact confidence intervals will be calculated using SAS PROC FREQ as follow:

```
PROC FREQ data=temp;
  tables resp/binomial (exact level='1');
RUN;
```

The lesion-level positive percent agreement and overall percent agreement will be calculated based on the number of lesions detected as positive by conventional scan and/or by PET scan.

These percent agreements will be calculated as follows with their two-sided 95% score confidence intervals:

- Positive percent agreement: $a/(a+c) * 100$
- Overall percent agreement: $(a)/(a+b+c) * 100$

Where

- a is the number of lesions detected as positive in both PET and conventional scan
- b is the number of lesions detected as positive in PET scan but not correlated with conventional scan
- c is the number of lesions detected as positive in conventional scan but not correlated with PET scan

These 2 coefficients and their 95% Clopper Pearson Exact confidence intervals will be calculated using SAS PROC FREQ as above.

Document: K:\AAA\Ga-PSMA-R2\VYA27826\Biostatistics\Documentation\SAP\v2.0\Ga-PSMA-R2-SAP_v2.0
 Author:  Version Number: 2.0

Version Date: 29JUN2020

Template No.: CS_TP_BS016 Revision 5
 Effective Date: 01Apr2018

Reference: CS_WI_BS005

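### In SAP 15.2.4 the patient-level cells b and c overlap with cell a, and the stated base leaves out the patients in cell d

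*SAP*

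**What the plan says.** SAP 15.2.4 crosses PET (+/-) with conventional scan (+/-) in a table with cells a, b, c and d and column totals a+c and b+d. Positive agreement is a/(a+c), negative agreement d/(b+d), and overall agreement (a+d)/(a+b+c+d).

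The cells are then defined in words:

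- Cell a needs a lesion on each scan, with no matching between lesions: "a is the number of patients with at least one positive lesion detected by conventional scan and at least one positive lesion" (the sentence ends by placing the second lesion on PET).
- Cell b turns on an unmatched PET lesion: "b is the number of patients with at least one positive lesion detected by PET scan that is not correlated with conventional scan".
- Cell c mirrors this from the conventional side: "c is the number of patients with at least one positive lesion detected by conventional scan that is not correlated with PET scan".
- Cell d holds the double-negative patients: "d is the number of patients with no lesions detected by conventional scan or PET scan".

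The base for the three percentages is given as follows: "number of patients with at least one positive lesion detected by conventional scan and/or at least one positive lesion detected by PET scan".

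The preceding section, SAP 15.2.3, counts positive patients by location and adds: "Note: A positive patient has at least 1 lesion detected". It also asks for this count: "The number of positive patients detected on the conventional scan, with no lesions correlated with any lesion detected on the PET scan".

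On the population, Protocol 4.1 (criterion 3a) admits PCa-BR patients "with corresponding CT/MRI or bone scan revealing absence of local recurrence or metastatic lesions".

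**The concern.** There are two separate defects.

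**Overlapping cells.** In the displayed table, b is PET-positive and conventional-negative, and c is the reverse. The written definitions ask only for one unmatched lesion and say nothing about the other scan. A patient with lesions on both scans, one of which has no counterpart, satisfies a and also b or c. With unmatched lesions of both kinds he satisfies all three. He is then scored as agreement and as disagreement, and the result depends on lesion matching rather than on patient status. The four cells can add up to more than the number of patients, and a binomial interval on that total treats one person as several.

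**Base without cell d.** A base of patients positive on at least one scan contains no double-negative patient. Yet d is the numerator of negative agreement and part of overall agreement.

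Per-patient agreement is a named secondary objective (Protocol 2.1.2, SAP 2.2). Two programmers working from this section could report different figures from the same data.

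**Working it through.** **1. The plan's own figure.** Protocol 8.1 gives the only number for patient-level agreement: 25 of 30 (83.3%), 95% CI 66.4% to 92.7%. The score interval with z = 1.96 (z² = 3.8415) reproduces it:

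- centre = (0.8333 + 3.8415/60) / (1 + 3.8415/30) = 0.7955
- half-width = 1.96 × √(0.8333 × 0.1667/30 + 3.8415/3600) / 1.1280 = 0.1311
- result: 66.4% to 92.7%

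The denominator there is all 30 patients, not only those positive on some scan.

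**2. Who can be counted twice.** Reading the definitions literally:

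| PET | Conventional | Cells met |
|---|---|---|
| + | − | b only (no PET lesion can be matched) |
| − | + | c only |
| − | − | d only, and outside the stated base |
| + | + | a; also b if a PET lesion is unmatched; also c if a conventional lesion is unmatched |

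Only double-positive patients are affected. Let u_b of them have an unmatched PET lesion and u_c an unmatched conventional lesion. With exclusive cells a, b, c, d summing to N, the literal text gives:

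- positive agreement = a / (a + c + u_c)
- negative agreement = d / (b + u_b + d)
- overall agreement = (a + d) / (N + u_b + u_c)

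All three can only fall or stay the same.

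**3. Assumed cohort.** The group sizes follow Protocol 3.1: about 6 + 12 = 18 PCa-BR and about 12 mPCa, 30 in total. The PCa-BR patients are taken as conventional-negative (criterion 3a) and the mPCa patients as conventional-positive. The PET results are assumptions: 10 of 12 mPCa and 9 of 18 PCa-BR positive. The exclusive cells are a = 10, b = 9, c = 2, d = 9.

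| Reading | Cell total | Positive | Negative | Overall |
|---|---|---|---|---|
| Exclusive cells (displayed table) | 30 | 10/12 = 83.3% | 9/18 = 50.0% | 19/30 = 63.3% |
| Literal, u_b = u_c = 1 | 32 | 10/13 = 76.9% | 9/19 = 47.4% | 19/32 = 59.4% |
| Literal, u_b = u_c = 5 | 40 | 10/17 = 58.8% | 9/23 = 39.1% | 19/40 = 47.5% |
| Literal, u_b = u_c = 10 | 50 | 10/22 = 45.5% | 9/28 = 32.1% | 19/50 = 38.0% |
| Literal, u_b = 10, u_c = 0 | 40 | 10/12 = 83.3% | 9/28 = 32.1% | 19/40 = 47.5% |
| Base sentence followed, no overlap (d removed) | 21 | 10/12 = 83.3% | 0/9 = 0% | 10/21 = 47.6% |

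**4. Effect on the interval.** The 95% score interval for overall agreement is 45.5% to 78.1% on 19/30 (width 32.6 points) and 25.9% to 51.8% on 19/50 (width 25.9 points). It becomes narrower although no patient has been added.

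**5. Base sentence.** With d removed, negative agreement is 0/b: zero for any data, and undefined if b = 0. Positive agreement does not use d and is unchanged.

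**The case against.** The strongest reply is that the displayed table shows the intent. Its column totals make sense only with exclusive cells, SAP 15.2.3 says what a positive patient is, and the PROC FREQ call uses a single response variable, which suits one record per patient. A careful programmer might simply follow the table. On the base, the sentence could be read as describing how positivity is determined, and the explicit formulas containing d would normally prevail over a loose introduction. The table templates mentioned in SAP section 8 are not among the documents and may settle the matter. The illustration is assumed throughout, and its extreme case needs every double-positive patient to have unmatched lesions of both kinds.

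Much of this is fair as to consequence. Double counting is what the text produces when followed, not a certainty, and its size is unknown. But each escape requires setting aside a written definition. The PROC FREQ call does not say how its variable is built, and it cannot hold a patient who is both a success and a failure for positive agreement.

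One further point stands in part. SAP 15.2.3 gives descriptive counts in which overlap is expected, so its different wording is not itself a contradiction. It does show that the SAP distinguishes having some unmatched lesion from having no matched lesion at all, and that b and c use the first, non-exclusive form.

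**Conclusion.** The concern holds on the text. The written definitions of b and c contradict the displayed table, and the stated base excludes patients whom two of the three formulas need.

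The size depends on data that the documents do not give. The overlap does nothing if no double-positive patient has an unmatched lesion. Otherwise an unmatched conventional lesion lowers positive agreement, an unmatched PET lesion lowers negative agreement, and either lowers overall agreement. In the assumed cohort, one patient with both kinds costs 6.4, 2.6 and 3.9 percentage points respectively (83.3 − 76.9, 50.0 − 47.4, 63.3 − 59.4). The overlap should fall mainly on the roughly 12 mPCa patients, because PCa-BR patients normally have no conventional lesion. The base error depends less on the data: if followed, negative agreement carries no information.

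This should be fixed, but its reach is limited. The endpoint is secondary and descriptive, no formal testing is planned (SAP 6.6), and the primary safety analysis is untouched.

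**What to change.** State in SAP 15.2.4 that each patient falls in exactly one cell, as in the displayed table:

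- a: at least one lesion on each scan
- b: at least one lesion on PET, none on conventional scan
- c: at least one lesion on conventional scan, none on PET
- d: none on either

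Replace the base with all FAS patients evaluable on both modalities, so that a+b+c+d = N. Protocol 9.2.1 already ties imaging evaluability to completion of the imaging protocol and can serve as the starting point; the SAP should add what counts as an evaluable conventional scan.

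State whether a patient positive on both scans with no matched lesion counts as agreement. If matching is meant to be a condition for a, write it as a rule that still assigns one cell per patient. Leave counts of matched and unmatched lesions to SAP 15.2.3 and the lesion-level analysis.

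The cost is about three sentences in the SAP and one derivation. If the table has already been programmed, it also needs a rerun.

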	 During the first part (Phase 1), approximately 6 patients with biochemically recurrent PCa will receive the investigational product (IP) and will remain at the site for approximately 6 hours post-injection in order to assess the PK, biodistribution vs. time, and dosimetry for critical organs. Patients will receive a single dose of 3 MBq/kg, (≥ 150 and ≤ 250 MBq), of ⁶⁸Ga-PSMA-R2 intravenously. Serial blood and urine samples will be collected for PK characterization and dosimetry and whole-body PET/CT will be acquired at selected time points (0-4 hours) to determine organ and tumor absorbed doses. Safety assessments will be conducted after IP administration on Day 1, and during follow-up on Days 7 and 28.
	• In the second part of the study (Phase 2), two groups of approximately 12 patients will be enrolled (patients with PCa in biochemical recurrence (PCa-BR), and patients with prostate cancer in the metastatic stage (mPCa)). Enrollment will be capped at 12 patients in each group to ensure an even distribution of patient conditions. If preliminary data analysis from the Phase 1 part of the study provides sufficient dosimetry data, all patients will undergo whole body PET/CT imaging optimized for time (up to 2 time points) according to the data analysis from the Phase 1 component of the study.
Study Population	Patients with histologically confirmed adenocarcinoma of prostate staged as PCa-BR or mPCa
Study Duration	Approximately 6 weeks: up to 2 weeks of screening assessment, a 1-Day IP administration and imaging period, and three safety follow-up visits, at least one hour after the administration, then 7 Days and 28 Days after the administration. End of the study is defined as the date the last patient enrolled completes the 28 Days safety follow-up.
Treatment Duration	One Day/single IP administration
Number of Patients	Approximately 30 patients will be enrolled in this trial.
Planned	Phase 1 will include approximately 6 patients with adenocarcinoma of prostate origin staged as PCa-BR.
	Phase 2 will be comprised of 2 groups: one of approximately 12 patients with PCa- BR and another of approximately 12 patients with mPCa.
Inclusion Criteria	1. Male patients, 18 years of age or older.
	2. Signed and dated written informed consent by the patient prior to any study- specific procedures
	3. Histologically confirmed adenocarcinoma of the prostate.

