3. STUDY DESIGN AND PATIENT POPULATION

3.1. Study Design

This is an open label, multi-center, single dose, Phase 1/2 study to evaluate the safety and tolerability of 3 MBq/Kg, but not less than 150 and no more than 250 MBq, of ⁶⁸Ga-PSMA-R2 in adult patients with PCa expressing PSMA receptors.

This study will consist of 2 phases.

Phase 1:

During the Phase 1 portion of the study, approximately 6 patients with biochemically recurrent PCa will receive the IP and will remain at the site for approximately 6 hours post-injection in order to assess PK, biodistribution, and dosimetry for critical organs. Patients will receive a single dose of 3 MBq/kg, (\geq 150 MBq and \leq 250 MBq), of ⁶⁸Ga-PSMA-R2. The product will be prepared prior to administration and injected intravenously and each patient will undergo a whole-body PET/CT scan following IP administration. Serial blood and urine samples will be collected for PK characterization and dosimetry. Safety assessments will be conducted after IP administration on Day 1, and during follow-up on Days 7 and 28.

Dosimetry will be assessed in 6 patients, they will undergo static whole-body PET/CT images at 0-4 hours to determine absorbed doses by the normal organs and target tumor lesions.

Phase 2:

Two groups of approximately 12 patients will be enrolled in the Phase 2 portion of the study (patients with PCa-BR, and mPCa). Enrollment will be capped at 12 patients in each group to ensure an even distribution of patient condition. If preliminary data analysis from the Phase 1 portion of the study provides sufficient dosimetry data, all patients will undergo whole body PET/CT imaging optimized for time according to the data analysis from the Phase 1 component of the study.

Patients who have signed the informed consent and are eligible for study participation according to the inclusion and exclusion criteria will receive a single intravenous bolus of ⁶⁸Ga-PSMA-R2 on Day 1.

This study is comprised of 4 clinical visits and will be conducted in 3 study periods including: Screening, administration/ imaging, and safety follow-up period (final/early termination).

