6. GENERAL CONSIDERATIONS

6.1. POPULATION SUMMARIZATION

In general, data will be presented by population.

- The following populations will be used in the analyses:

Document:	K:\AAA\Ga-PSMA-R2\VYA27826\ Biostatistics\Documentation\SAP\v2.0\Ga-PSMA-R2-SAP_v2.0
Author:	[Redacted] Version Number: 2.0
Template No.:	CS_TP_BS016 Revision 5
Effective Date:	01Apr2018
Version Date:	29JUN2020
Reference:	CS_WI_BS005

- PCa-BR
- mPCa
- The PCa-BR population group will also be presented separately for Phase I and Phase II patients.

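### Lesion-level agreement in SAP 15.2.4 gets a plain binomial interval that ignores clustering of lesions within patients, and the section names two interval methods for the same coefficients

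*SAP*

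**What the plan says.** The lesion-level analysis is in SAP 15.2.4, after the patient-level one. "The lesion-level positive percent agreement and overall percent agreement will be calculated based on the number of lesions detected as positive" by either scan. Cell a counts lesions positive on both scans, b those on PET only, and c those on conventional imaging only. Positive percent agreement (PPA) is a/(a+c) and overall agreement is a/(a+b+c).

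On the interval, the section first says "These percent agreements will be calculated as follows with their two-sided 95% score confidence intervals", and then, for the same two coefficients, "These 2 coefficients and their 95% Clopper Pearson Exact confidence intervals will be calculated using SAS PROC FREQ as above". The code referred to is the patient-level call, "tables resp/binomial (exact level='1", which has no patient identifier, cluster or stratum. The patient-level text has the same double naming: the score sentence, followed by "These 3 coefficients and their 95% Clopper Pearson Exact confidence intervals will be calculated using SAS PROC FREQ as follow".

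Four other places bear on this:

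- **Group sizes.** Protocol synopsis: "Phase 1 will include approximately 6 patients with adenocarcinoma of prostate origin staged as PCa-BR". Protocol 3.1 adds about 12 biochemical-recurrence (BR) and about 12 metastatic (mPCa) patients in Phase 2.
- **Eligibility.** Inclusion criterion 3a (Protocol 4.1) requires BR patients to have conventional imaging without lesions.
- **Lesion cap.** The only cap, 10 per patient, is for Phase 1 dosimetry (Protocol 6.5.4.2). None is stated for the agreement analysis.
- **Columns.** SAP 6.1 presents BR and mPCa separately and adds: "The PCa-BR population group will also be presented separately for Phase I and Phase II patients".

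**The concern.** A binomial interval is valid for independent trials. Lesions in one patient share tumour biology, scanner, reader and scan timing, so their agreement status is likely to be correlated. The information then lies closer to the number of patients than to the number of lesions.

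The design makes the number of patients small. BR patients enter with negative conventional scans, so the PPA denominator a+c rests mainly on about 12 mPCa patients, however many lesions they carry. Overall agreement adds about 18 BR patients (6 + 12) whose lesions should be nearly all PET-only, so in the Overall column it pools two groups with very different agreement.

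A few patients with many lesions could dominate the estimate while the printed interval suggests good precision. The two method names add a smaller problem: the text does not say which interval is to be reported.

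**Working it through.** **1. The plan's own figure.** Protocol 8.1 gives 66.4% to 92.7% for 25/30. The score interval is [p + z²/2n ± z√(p(1−p)/n + z²/4n²)] / (1 + z²/n). With p = 0.8333, n = 30 and z = 1.96, this is (0.8974 ± 0.1479)/1.1281 = 66.4% to 92.7%, which reproduces it. Clopper-Pearson, the method in the SAP code, gives 65.3% to 94.4%. For 48/60, score gives 68.2% to 88.2% and exact 67.7% to 89.2%. The method conflict therefore moves these limits by 0.5 to 1.7 points.

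**2. Width under clustering.** The design effect is DE = 1 + (m − 1) × ICC for m lesions per patient, and the effective sample size is n/DE. Take 12 patients with 5 lesions each, 50/60 agreeing (assumed). Plain exact limits are 71.5% to 91.7%. At ICC 0.3, DE = 1 + 4 × 0.3 = 2.2 and the effective n is 60/2.2 = 27.3. Exact limits at that n are 64.2% to 94.7%, or 30.5/20.2 = 1.5 times as wide.

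**3. Coverage of the planned interval for PPA.** Beta-binomial simulation, 20,000 replicates per setting, 12 patients, true agreement 80%. Lesion counts are equal, or geometric with minimum 1 (unequal). Lesion numbers, their spread and the ICC are assumptions. Entries are % coverage of the nominal 95% exact interval, equal / unequal counts:

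| ICC | mean 3 lesions | mean 5 | mean 10 |
|---|---|---|---|
| 0 | 96.5 / 97.1 | 96.6 / 96.8 | 96.2 / 96.3 |
| 0.1 | 94.8 / 93.5 | 92.8 / 89.2 | 86.4 / 80.1 |
| 0.3 | 90.6 / 86.1 | 84.3 / 76.5 | 71.1 / 60.7 |

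The score interval does not help. In a separate run at true agreement 83.3% (12 patients, 5 lesions each, ICC 0.3), exact covered 83.9% and score 80.8%.

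**4. Overall agreement, Overall column.** Add 18 BR patients with a Poisson number of PET-only lesions, mean q. The target is 12m(0.8)/(12m + 18q). With q = 1 this is 28.8/54 = 53%, 48/78 = 62% and 96/138 = 70% for m = 3, 5 and 10. Coverage of the plain exact interval, equal / unequal mPCa counts:

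| ICC | m = 3 | m = 5 | m = 10 |
|---|---|---|---|
| 0.1 | 97.6 / 93.1 | 95.2 / 89.2 | 90.2 / 80.8 |
| 0.3 | 96.0 / 89.5 | 91.2 / 81.3 | 78.8 / 66.7 |

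At m = 5 and ICC 0.3, q = 0.5 gives 88.7 / 81.1 and q = 2 gives 93.6 / 79.9. If every BR patient has exactly one lesion, equal counts give 95.4, which is nominal.

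**5. BR columns.** With a near 0, overall agreement might be 0/18, whose exact limits are 0 to 18.5%. If a + c = 0, PPA is undefined.

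**The case against.** The strongest case concerns weight. Lesion-level agreement is a SAP addition: Protocol 8.2.3 plans agreement at patient level, summarised descriptively. SAP 6.6 rules out formal testing, and no sample size or decision uses this interval. Patient-level results stand beside it and are unaffected by lesion clustering. All of that is right and limits the severity.

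The size rests on assumed inputs. That is also right: at 3 lesions and ICC 0.1 there is no real problem, and the lowest coverages need ICC 0.3 with unequal counts averaging 5 to 10 lesions. The documents support the direction of the error, not its amount.

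SAP 6.1 gives mPCa its own column, so the mixing of groups affects only the Overall column. This stands, but clustering within mPCa patients remains in the mPCa column too.

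The clustered alternative is itself approximate with about 12 patients, and it reverts to the unadjusted interval when all or no lesions agree. This is a fair reason to prefer dropping the interval.

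Finally, the code and its lead-in both say Clopper-Pearson, so a programmer following the code has one answer. True, but the text still gives two instructions, and the protocol's worked example follows the other one.

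**Conclusion.** Both parts hold. The lesion-level interval treats pooled lesions as independent and is too narrow under positive within-patient correlation. For PPA with 12 mPCa patients and 80% agreement, coverage ranges from about nominal (3 lesions, ICC 0.1) through 84% / 77% (5 lesions, ICC 0.3) to 71% / 61% (10 lesions, ICC 0.3), for equal / unequal counts. Lesion counts, spread, ICC and the 80% are assumptions. The existence of the gap is certain and its size is not.

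The naming conflict is plain on the page and small in effect. The impact overall is minor to moderate: no planned conclusion changes, but a reported 95% interval could overstate what about 12 patients can show. It should be corrected because correction is cheap.

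**What to change.** At lesion level, do one of two things.

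- **(a) Drop the interval.** Report counts and percentages, with the number of contributing patients beside each denominator. This is the simpler choice and needs no new code for an interval.
- **(b) Use a patient-clustered interval.** Replace the PROC FREQ binomial with Clopper-Pearson limits on the design-effect-adjusted effective sample size, with patient as cluster, t-based degrees of freedom and the design effect floored at 1 (PROC SURVEYFREQ with a CLUSTER statement). When all or no lesions agree, give unadjusted exact limits and footnote them as such. When the denominator is zero, print *not estimable*. Both cases are foreseeable in the BR columns.

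The cost of (b) is a few lines of SAS and intervals about 1.2 to 2.4 times as wide (12 patients, 80% agreement, ICC 0.1 to 0.3). Its coverage in those settings is 92% to 99%, and at ICC 0 it is conservative (98% to 99%). At 90% agreement it can fall to 89% within the same ICC range. The worst case simulated was 84%, at 10 unequal lesions and ICC 0.5, where the plain interval gives 51%. In the Overall column with one BR lesion on average and ICC 0.1 to 0.3, it covers about 96% to over 99% if mPCa agreement is 80%, and 92% to 98% if it is 40%.

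At both levels, name one interval method and make text and code match. At patient level, score would agree with the example in Protocol 8.1. This is a wording change plus, if score is chosen, a change of option in the code.
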